### 3. Introduction

#### 3.1. Study Rationale

The Diabetes Control and Complications Trial (DCCT) and its observational Epidemiology of Diabetes Interventions and Complications (EDIC) follow-up study demonstrated that intensive therapy (that lowers glycemia) reduced renal and cardiovascular disease, the predominant causes of early mortality in patients with type 1 diabetes mellitus (T1DM) (Nathan et al. 2005; DCCT/EDIC Research Group et al. 2011).

The availability of insulin pumps and continuous glucose monitors has transformed diabetes care by allowing continuous infusion of insulin with bolus doses administered based on food intake. Hypoglycemia may result from excessive insulin administration in relation to food intake, disease state, or physical activity. Hypoglycemia may be life-threatening; this is a risk with any insulin administration, and may be of concern with automated systems.

An artificial pancreas device system (APDS) may provide better control of blood sugar with less episodes of hypoglycemia. A bihormonal APDS combines automated delivery of both insulin and glucagon. Pilot studies using investigational, bihormonal APDSs have demonstrated that delivery of small doses of glucagon in response to declining glucose levels reduces the frequency of hypoglycemia (Russell et al. 2012). Glucagon is a 29-aminoacid peptide hormone produced in the pancreas that stimulates glucagon receptors in the liver, resulting in the breakdown of stored glycogen into glucose. Glucagon opposes the effects of insulin in the liver and increases blood glucose levels.

The current commercial glucagon (recombinant glucagon [rGlucagon]) preparations are only available as lyophilized powder that must be reconstituted with a diluent before administration. The current Lilly formulation of rGlucagon also has poor solubility in CCI [REDACTED]

LY3185643 is a glucagon analog with improved solubility that is being developed for use in a bihormonal APDS. The current study is designed to assess the pharmacokinetic (PK) and pharmacodynamic (PD) profiles of LY3185643 and compare these to rGlucagon. Understanding the relative potency of these molecules, as well as any differences in time-action profiles, will be used to direct modifications of APDS control algorithms that have been developed based on rGlucagon pharmacology. These modified control algorithms will be tested in future studies using LY3185643 in an investigational, bihormonal APDS.

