#### 3.2. Background

LY3185643 is a selective glucagon analog with potency similar to rGlucagon based on nonclinical studies (in vitro and in vivo). LY3185643 administration resulted in dose-dependent increases in blood glucose levels in the CCI [REDACTED] in vivo following subcutaneous (SC) dosing in a similar time pattern as rGlucagon. Peak glucose level was attained at 30 minutes and the glucose level returned to baseline at approximately 60 minutes postadministration as observed with rGlucagon.

The PK of LY3185643 was evaluated in rats and dogs. Exposure increased with increase in dose. LY3185643 exposure in dogs was generally dose proportional. No consistent sex differences in systemic exposure were observed in rats or dogs. The time to maximum drug concentration ( $T_{max}$ ) ranged from approximately CCI in dogs. The half-life ( $t_{1/2}$ ) of LY3185643 following SC administration in dogs ranged from approximately CCI.

Development of LY3185643 was supported by repeat-dose nonclinical studies in both rats and dogs receiving daily SC injections for approximately 1 month. No adverse findings were reported following the 1-month nonclinical toxicology studies in both rats and dogs.

Administration of LY3185643 CCI decreased blood pressure and increased heart rate (refer to the LY3185643 Investigator's brochure [IB]), consistent with the acute effects of native and/or recombinant glucagon peptides previously described in dogs (CDER 1998; Eistrup et al. 1993). No other LY3185643-related cardiovascular changes were noted. The reported changes in animal physiology were consistent with the pharmacologically-related changes associated with repeated administration of native and/or recombinant glucagon peptide described previously (Root 1954; CDER 1998; Eistrup et al. 1993).

Further, signs of injection-site inflammation were observed in dogs at all doses which were attributed of the frequency of repeat SC administration; however, there were no local tolerance issues observed in the nonclinical repeat-dose studies.

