9.4 Pharmacodynamic Assessment

9.4.1 Pharmacodynamic Analysis

The PD time-action and response of LY3185643 and rGlucagon will be compared to establish the relative potency between LY3185643 and rGlucagon.

The primary PD response variables of interest include t_{max} , C_{max} , change from baseline in C_{max} and change from baseline to each time point, and incremental AUCs for glucose measured by YSI glucose analyzer and C-peptide. Similar PD response variables using laboratory measured glucose will also be estimated.

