9.4.2 Pharmacodynamic Statistical Methodology

All PD parameters including the baseline-corrected parameters will be summarized by dose group and tabulated. The individual observed and mean (by dose group) time profile of the PD measurements after dosing will be plotted.

For these parameters, a linear model will be fitted to account for the PD difference between LY3185643 and rGlucagon. The model is detailed below. In addition, partial AUC for glucose over appropriate time intervals will be calculated using the trapezoidal rule. The AUC for each subject after each dose will also be baseline-adjusted. Baseline for each dose will be defined as the average of predose values for that dose.

For each PD parameter, the linear model that is proposed to account for differences between LY3185643 and rGlucagon is:

$$Y_{kl} = \beta_0 + \beta_1 d_{kl} + \beta_2 d_{kl} * Z_{kl} + u_k + e_{kl} \quad (1)$$

where k denotes the subject index, l denotes the period index, d_{kl} is the dose in mg during each period, Z_{kl} is the treatment indicator (0 for rGlucagon and 1 for LY3185643), $u_k \sim NI(0, \sigma_{u^2})$ denotes the between subject error, and $e_{kl} \sim NI(0, \sigma_{e^2})$ denotes the within-subject error. The

notation “NI” means “Normally Independent.” There is no term for the treatment group indicator Z_{kl} because at dose = 0 the response should be the same for both treatment groups. Setting the mean responses for each treatment equal to each other, it follows that:

$$\beta_0 + \beta_1 D_1 + \beta_2 D_1 = \beta_0 + \beta_1 D_0$$

where D_0 denotes the rGlucagon dose and D_1 denotes the LY3185643 dose. It follows that $D_1 = \lambda D_0$ where $\lambda = \beta_1/(\beta_1 + \beta_2)$ is the conversion factor that determines how many mg of LY3185643 are equivalent to one mg of rGlucagon. The model (1) can be reparameterized as a nonlinear mixed model:

$$Y_{kl} = \beta_0 + \beta_1 d_{kl} + (1 - \lambda)/\lambda \beta_1 d_{kl} * Z_{kl} + u_k + e_{kl}.$$

Then, the conversion factor λ (the point estimate and the 90% confidence interval) will be directly estimated from this nonlinear model. This model may be extended to allow for multiple parameter values, if deemed appropriate.

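### The SAP's common-intercept conversion-factor model should not be fitted to t_max: equal response at dose 0 does not apply to a peak time, so any constant timing offset is read as potency

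*SAP*

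**What the plan says.** SAP Section 9.4.1 puts t_max in the list of primary PD response variables, for YSI glucose and for C-peptide. The same list includes "change from baseline to each time point, and incremental AUCs for glucose measured by YSI glucose analyzer". Section 9.4.2 then states: "For each PD parameter, the linear model that is proposed to account for differences between LY3185643 and rGlucagon is" Y = β0 + β1·d + β2·d·Z plus a subject effect and error, where d is dose in mg and Z is 1 for LY3185643. From this it reports λ = β1/(β1+β2), the mg of LY3185643 equivalent to 1 mg of rGlucagon, with a 90% CI. No PD variable is exempted.

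There is no main effect of treatment, "because at dose = 0 the response should be the same for both treatment groups". On combining parameters the SAP says: "This model may be extended to allow for multiple parameter values, if deemed appropriate". Neither document says whether t_max would enter such an extension.

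Other output on timing is descriptive: "All PD parameters including the baseline-corrected parameters will be summarized by dose group and tabulated", and individual and mean time profiles are plotted.

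Protocol Section 3.1 treats timing as a question beside potency: relative potency, "as well as any differences in time-action profiles, will be used to direct modifications of APDS control algorithms".

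**The concern.** The dose-0 argument works for quantities that shrink to a common value as dose falls, such as incremental AUC or change from baseline in Cmax. A peak time does not behave that way. With no dose there is no drug-induced peak, so nothing makes the two t_max lines meet at d = 0. The design has no zero dose (Protocol Table APCA.5.1), so the shared intercept is an extrapolation below 10 µg.

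If one drug peaks later than the other by a roughly constant number of minutes, the model has no term for it. The offset goes into the dose slopes and comes out as a potency ratio. A reader would then see a t_max conversion factor in mg per mg that partly reflects timing, with no interval in minutes beside it. Timing is one of the two things the protocol wants for the control algorithms.

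**Working it through.** The plan gives no figure for t_max under this model, so there is nothing of its own to reproduce. The check asks what λ converges to on the planned doses.

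**Inputs from the documents.** LY3185643 0.01, 0.025, 0.05, 0.1, 0.2 mg; rGlucagon 0.01, 0.025, 0.05, 0.2 mg; 18 completers receiving all nine doses.

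**Assumed inputs.** Offset δ (LY3185643 minus rGlucagon, min); rise in t_max over 10 to 200 µg of 19 or 57 min, so slope s = rise/0.19 = 100 or 300 min/mg; within-subject SD 10, 15 or 30 min. The documents give none of these.

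**1. Where one minute of offset goes.** Every completer has the same nine doses, so the random-intercept fit has the same slopes as least squares.
- rGlucagon: Σd = 0.285, Σd² = 0.043225, (Σd)²/Σd² = 1.879.
- LY3185643: Σd = 0.385, Σd² = 0.053225, (Σd)²/Σd² = 2.785.
- Shift c in the common intercept: c·(9 − 1.879 − 2.785) = 5 − 2.785, so c = 0.511.
- rGlucagon slope: −0.511 × 0.285/0.043225 = −3.37 min/mg.
- LY3185643 slope: (1 − 0.511) × 0.385/0.053225 = +3.54 min/mg.

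**2. Effect on λ when the true ratio is 1.** λ = (s − 3.37δ)/(s + 3.54δ).

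| Rise | δ = −10 | δ = 0 | δ = +10 |
|---|---|---|---|
| 57 min | 333.7/264.6 = 1.26 | 1.00 | 266.3/335.4 = 0.79 |
| 19 min | 133.7/64.6 = 2.07 | 1.00 | 66.3/135.4 = 0.49 |

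With δ = 0 and a linear non-zero slope, λ is unbiased, also when the true ratio is not 1 (0.80 returns 0.80; 1.25 returns 1.25).

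**3. t_max flat in dose (s = 0).** λ = −3.37/3.54 = −0.95 for any non-zero δ, set by the dose grid alone. For δ = 0 it is 0/0. In simulation with no slope and no offset (18 completers, SD 15 or 30), the LY3185643 slope could not be distinguished from zero in about 90% of trials, so the interval for λ is unbounded.

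**4. Coverage of λ = 1 by the nominal 90% interval.** This equals the chance that the interval for β2 includes 0. The bias in β2 is 3.54 + 3.37 = 6.91 min/mg per minute of offset, whatever the slope. In 4000 simulated trials per setting, at SD 10/15/30 min:
- no offset: about 90%;
- 5 min offset: about 28/56/80%;
- 10 min offset: under 1%, about 10%, about 55%.

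**5. What replacement summaries can show.**
- *Equal-mg difference.* With no offset and LY3185643 slope p·s, the difference at dose d is s·(p − 1)·d. Mean shared dose = 0.285/4 = 0.07125 mg. For the 57 min rise the four-dose mean is −10.7 min at p = 0.5 and +21.4 min at p = 2. At p = 0.5 it is −1.5 min at 10 µg and −30 min at 200 µg.
- *Separate-intercept linear model.* If t_max is linear in dose, it recovers δ. If t_max is linear in log dose (57 min rise, no offset), it returns a false delay of −11.9 min at half potency and +14.5 min at double potency.

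**6. Precision of the equal-mg difference.** 90% half-width with t(0.95, 17) = 1.740, at SD 10/15/30:
- single dose, 1.740·SD·√2/√18: 5.8/8.7/17.4 min;
- four-dose mean, 1.740·SD·√(2/4)/√18: 2.9/4.3/8.7 min.

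These assume independent errors and ignore rounding to the sampling grid.

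**The case against.** The strongest reply is that no offset has been shown. The one comparison of timing, nonclinical, says LY3185643 raised glucose after subcutaneous "dosing in a similar time pattern as rGlucagon" (Protocol Section 3.2). If there is no offset and t_max changes linearly with dose, λ is correct. This stands. It limits what can be said about size, but it does not supply a reason for the shared intercept, and the flat-dose problem arises with no offset at all.

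t_max is not an endpoint in Protocol Table APCA.4.1, no decision rule hangs on its λ, and a value such as −0.95 would be recognised as meaningless. This also stands and lowers the priority.

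The plan is not blind to timing. t_max is tabulated by dose, profiles are plotted, and changes at each time point are analysed. What is missing is an interval for a t_max difference in minutes.

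The obvious replacements also mix potency with delay (step 5). This is correct. The equal-mg difference must be labelled for what it is, and a separate-intercept model cannot be offered as a clean estimate of delay without a check of linearity.

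A reader might add that Protocol Section 10.3.3.2 lists treatment as a fixed effect while SAP Section 11 declares no changes. That is a separate documentation point. It concerns every PD parameter, the protocol allows the SAP to specify otherwise, and Section 9.4.2 states its reason openly. It adds nothing to the t_max argument.

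**Conclusion.** The point holds in a limited form. As written, the SAP fits the common-intercept model to t_max on a rationale that does not apply to a peak time. The resulting λ is biased by any constant offset, in a direction that depends on which drug peaks later, and it is undefined if t_max is flat in dose with no offset. For a 10 min offset and a true ratio of 1, λ is 0.79 or 1.26 with a 57 min rise, and 0.49 or 2.07 with a 19 min rise. Offset, rise and SD are assumptions.

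Two stronger readings are not supported. One is that the drugs do peak at different times, so the t_max λ will be wrong: the documents report a similar nonclinical pattern and otherwise leave the question open. The other is that the potency conversion as a whole is compromised: the separate λ values for Cmax and AUC, the PD endpoints in Table APCA.4.1, are unaffected. A combined λ would be affected only if t_max were included in it. Priority is low to moderate.

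**What to change.** In SAP Section 9.4.2:

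- Exclude t_max from the λ model and from any multi-parameter extension.
- Alongside the planned tables and plots, report the within-subject LY3185643 minus rGlucagon difference in t_max, in minutes with a 90% CI, at each shared dose (10, 25, 50, 200 µg) and averaged over the four, for glucose and for C-peptide. Show the per-dose results, because any mixing with potency can vary with dose.
- Label these as equal-mg contrasts. They describe the time-action difference at the same dose and do not separate delay from potency.
- Note that the sampling grid limits them, more so for C-peptide (5, 15, 30, 60 and 120 min post-dose) than for YSI glucose (13 post-dose times to 180 min).
- Do not present a separate-intercept linear model as evidence of a pure delay unless linearity of t_max in dose has been checked.

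The cost is SAP wording and a few extra table rows. All the data are already collected under the protocol.

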### **3.2.1. Clinical Experience**

LY3185643 has been administered SC to 27 healthy subjects as single doses of 0.01 mg, 0.03 mg, 0.05 mg, 0.06 mg, 0.1 mg, 0.2 mg, 0.3 mg, 0.48 mg, and 0.72 mg (n = 3 subjects for each dose level). Preliminary PK data available for doses up to 0.2 mg show dose-dependent increases in LY3185643 exposures. Over the dose range of 0.01 to 0.2 mg, the median time to peak concentrations ranged between 0.5 to 1.25 hours, mean peak concentrations ranged between 0.13 to 4.25 ng/mL, and mean terminal  $t_{1/2}$  ranged between 0.5 to 0.75 hours. LY3185643 concentrations decreased below the limit of quantification by 4 hours postdose. Dose-dependent increases in glycemic response were observed up to 0.2-mg dose level. Maximum mean blood glucose elevations of up to 180 mg/dL were observed at doses above 0.2 mg of LY3185643. Peak glucose concentrations were reached between 0.5 to 2 hours postdose, and glycemic effects lasted for up to 3 hours postdose. This transient glycemic effect at high LY3185643 concentrations is consistent with rGlucagon findings and likely reflects a feedback inhibition of hepatic glucose output in response to exogenous glucagon administration (Mighiu et al. 2013).

Adverse events (AEs) included nausea, vomiting, light headed, headache, dizziness, vasovagal episode, erythema at injection site, loose stools, feeling hot and cold, abrasion of right leg, increased appetite, right thigh ache, drowsiness, feels sleepy, feels faint, decreased alertness, and dehydration. The most common (67% of 36 reported events) AEs were nausea (n=10), vomiting (n=6), headache (n=3), dizziness (n=3), and light headedness (n=2). No serious AEs (SAEs) were noted.

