## 5. Study Design

### 5.1. Overall Design

This study is a Phase 1, single-center, subject- and investigator-blind, randomized, 9-way, 3-period crossover study in healthy subjects to evaluate the PK and PD of LY3185643 and rGlucagon after SC administration.

Up to 37 healthy men and women may be enrolled to target approximately 18 subjects to complete the study. Each subject will receive 3 doses on each of 3 dosing days (total of 9 doses: 5 doses of LY3185643 and 4 doses of rGlucagon) administered SC. Doses will be administered in a 9-way complete crossover design in 3 periods, and subjects will be randomized to predefined treatment sequences. Completers are defined as subjects who have received all 9 doses.

Subjects will be required to attend the CRU on at least 5 occasions:

- 1 screening visit (may occur up to 28 days before randomization)
- 3 treatment periods
- 1 follow-up visit (at least 30 days after completing the last dose of study treatment)

Each study period will consist of 3 days (Days -1 to 2). Subjects should return for the next period with a minimum of 3 days between treatment periods.

On Day -1, subjects will be admitted to the CRU. Subjects will be provided a carbohydrate-rich meal in the evening at approximately 10:00 PM and will remain fasted until completion of the study procedures on Day 1.

On Day 1, study drug will be administered SC as follows:

- Dose 1: morning of Day 1
- Dose 2: approximately 4 hours after administration of the first dose
- Dose 3: approximately 4 hours after administration of the second dose

Blood samples will be collected for the determination of concentrations of LY3185643, glucagon, glucose, C-peptide, and for immunogenicity as shown in the Schedule of Activities (Section 2).

Safety data will include clinical examinations, vital signs, electrocardiograms (ECGs; including telemetry), clinical laboratory tests, and a record of AEs.

All study procedures will end approximately 4 hours after the third dose. Subjects will be provided dinner and stay overnight in the CRU for observation. Subjects will be discharged the following day (Day 2) after completion of all assessments as shown in the Schedule of Activities (Section 2).

Figure [APCA.5.1](#) illustrates the study design.

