## 5.4. Scientific Rationale for Study Design

A population of healthy subjects is selected based upon the likelihood of less physiologic variability in the absence of disease states that may affect multiple organ systems and the absence of other confounding factors such as concomitant medications. Furthermore, studies with native glucagon suggest that the PD responses being assessed in this study are similar between healthy subjects and subjects with diabetes who form the eventual patient population for this treatment (Nielsen et al. 1997; Matsuda et al. 2002).

Three doses of LY3185643 and/or rGlucagon will be administered on Day 1 of each study period; each dose will be separated by at least 4 hours. A 4-hour dosing cycle is considered appropriate because previous clinical data support that a 4-hour observation period is a sufficient amount of time to obtain both the PK and PD profiles. The study drug concentrations will be below the quantification limits by 4 hours and the glycemic levels will return back to baseline within 4 hours postdose. A previous study used a similar design with up to 4 doses given over the course of a single day and showed that this dosing schedule was well tolerated and that the PD response was not attenuated or refractory to repeat dosing (Blauw et al. 2016).

The use of a crossover design allows each subject to serve as his or her own control, thereby reducing variability.

The currently marketed glucagon product, rGlucagon, will be administered to provide a comparison of its PK/PD profile to the PK/PD profile of LY3185643.

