**Table APCA.7.1. Investigational Product Regimens**

Product:	LY3185643	rGlucagon (recombinant glucagon)
Dose range:	10 to 200 µg	10 to 200 µg
Route of administration:	subcutaneous injection	subcutaneous injection

The investigator or designee is responsible for:

- explaining the correct use of the investigational product to the site personnel
- verifying that instructions are followed properly
- maintaining accurate records of investigational product dispensing and collection
- returning all unused medication to Lilly or its designee at the end of the study

**Note:** In some cases, sites may destroy the material if, during the investigative site selection, the evaluator has verified and documented that the site has appropriate facilities and written procedures to dispose of clinical trial materials.

Subjects will be instructed to contact the investigator as soon as possible if he or she has a complaint or problem with the investigational product so that the situation can be assessed.

Study treatment will be drawn up into a 0.3-mL insulin syringe with a 6-mm/31 G needle to ensure all injections are delivered to a consistent depth target into the SC space. Each syringe will be labelled appropriately and dispensed to qualified site personnel for administration.

The doses will be administered SC in the CRU by qualified site personnel (as designated by the investigator). Injection sites selected should be approximately 5 cm from the umbilicus and the treatment administered SC with the needle applied at approximately 90 degrees without pinching the skinfold. Each injection in a given study period will be administered into a different quadrant of the anterior abdominal wall (that is, left upper quadrant, left lower quadrant, and right upper quadrant) and the site of injection for each dose will be recorded. As far as it is

practical, the same staff will administer the injections. Please refer to the pharmacy binder for detailed instructions.

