### **10.3.3.2. Pharmacodynamic Statistical Inference**

PD parameters of interest may be transformed before statistical analysis if deemed necessary. Unless specified otherwise, parameters will be analyzed using a nonlinear mixed-effects model with period, treatment (LY3185643 or rGlucagon), and dose (within treatment) as fixed effects, baseline glucose as a covariate, and subject as a random effect. The use of other influencing variables as covariates will be explored as detailed in the statistical analysis plan.

A conversion factor will be defined in the model for each parameter to estimate the relative potency of LY3185643 to rGlucagon. In addition, a conversion factor will be estimated between LY3185643 and rGlucagon for multiple parameters simultaneously using a similar mixed nonlinear model approach to account for the correlation between parameters for the same subject. Model details will be discussed in the statistical analysis plan.

All PD parameters including the baseline-corrected parameters will be summarized by dose group and tabulated. Summary statistics will be provided. The individual observed and mean (by dose group) time profile of the PD measurements after dosing will be plotted.

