5. STUDY DESIGN

This study is a Phase 1, single-center, subject- and investigator-blind, randomized, 9-way, 3-period crossover study in healthy subjects to evaluate the PK and PD of LY3185643 and rGlucagon after subcutaneous (SC) administration.

Up to 27 healthy men and women may be enrolled to target approximately 18 subjects to complete the study. Each subject will receive 3 doses on each of 3 dosing days (total of 9 doses: 5 doses of LY3185643 and 4 doses of rGlucagon) administered SC. Doses will be administered in a 9-way complete crossover design in 3 periods, and subjects will be randomized to predefined treatment sequences. Completers are defined as subjects who have received all 9 doses.

Subjects will be required to attend the Clinical Research Unit (CRU) on at least 5 occasions:

- 1 screening visit (may occur up to 28 days before randomization)
- 3 treatment periods
- 1 follow-up visit (at least 30 days after completing the last dose of study treatment)

Each treatment period will consist of 3 days (Days -1 to 2). Subjects should return for the next period with a minimum of 3 days between treatment periods. On Day -1, subjects will be admitted to the CRU. Subjects will be provided a carbohydrate-rich meal in the evening at approximately 10:00 PM and will remain fasted until completion of the study procedures on Day 1. On Day 1, study drug will be administered SC as follows:

- Dose 1: morning of Day 1
- Dose 2: approximately 4 hours after administration of the first dose
- Dose 3: approximately 4 hours after administration of the second dose

Blood samples will be collected for the determination of concentrations of LY3185643, glucagon, glucose, C-peptide, and for immunogenicity as shown in the Schedule of Activities. Blood samples for measurement of glucose concentrations using YSI glucose analyzer will also be collected.

Safety data will include clinical examinations, vital signs, elec trocardiograms (ECGs; including telemetry, holter monitoring), clinical laboratory tests, concomitant medications and a record of adverse events (AEs).

All study procedures will end approximately 4 hours after the third dose. Subjects will be provided dinner and stay overnight in the CRU for observation. Subjects will be discharged the following day (Day 2) after completion of all assessments as shown in the Schedule of Activities.

Figure 1 illustrates the study design:

Period 1				Periods 2 and 3			Summary			
	Day -1	Day 1			Day 2					

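### The PD model for the conversion factor has no term for dose number within the day, so any within-day drift is counted as residual error and makes the 90% CI too wide

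*SAP*

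**What the plan says.** SAP section 5 states that "Each subject will receive 3 doses on each of 3 dosing days", with "Dose 2: approximately 4 hours after administration of the first dose"; protocol 5.1 adds "Dose 3: approximately 4 hours after administration of the second dose". Protocol 6.3.1 makes the fast run unbroken from before the first dose to 4 hours after the last. The Schedule of Activities and protocol 5.4 make 4 hours a minimum interval, while 5.1 calls it approximate; these statements should be reconciled.

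SAP 9.4.2 fits, for each PD parameter, Y = β0 + β1·d + β2·d·Z + subject + error, and derives λ = β1/(β1 + β2) with a 90% CI. Its notation reads "where k denotes the subject index, l denotes the period index, d_{kl} is the dose in mg during each period", although a period holds three doses. Protocol 10.3.3.2 plans a model "with period, treatment (LY3185643 or rGlucagon), and dose (within treatment) as fixed effects", with baseline glucose as covariate. It leaves further covariates to the SAP, which names none. Neither model has a term for dose number within the day.

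Protocol 5.4 justifies the 4-hour interval from previous clinical data and cites an earlier study of up to four doses in a day in which "the PD response was not attenuated or refractory to repeat dosing". Drug, glucose and C-peptide are sampled before every dose. The planned summaries are by treatment or dose group; none is by dose number or by preceding dose.

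**The concern.** Dose number within the day is a design factor known in advance. With a meal at about 10 PM and the example dosing times of 8 AM, 12 PM and 4 PM, the fast has lasted about 10, 14 and 18 hours at the three doses. On the approximate 8-hour figure in protocol 6.3.1 it is 8, 12 and 16 hours. Doses 2 and 3, two thirds of all profiles, also follow one or two glucagon-type doses with no food in between, and protocol 3.1 says glucagon acts by breaking down stored glycogen. A systematic difference between first and third doses is therefore plausible. A period term would not absorb it, because it lies within a day.

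λ and its interval are the relative-potency result that is meant to direct changes to the device control algorithms (protocol 3.1). At stake are the precision of that result and a planned check that the 4-hour interval was long enough.

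**Working it through.** The plan states no precision or power figure, so there is none to reproduce. The steps below use the example sequences in Table APCA.5.1 with 18 completers (two per sequence).

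**1. Balance.** 18 subjects × 9 doses = 162 profiles, of which 108 are second or third of the day. Over the nine sequences each treatment occurs three times as first, three times as second and three times as third dose. Dose number therefore has zero correlation with d and with d·Z.

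**2. SE of λ with no drift.** Assumptions not in the documents: linear response of 60 mg/dL at 0.2 mg, so β1 = 300 mg/dL per mg; true λ = 1 (β2 = 0); within-subject SD 10 mg/dL. At λ = 1 the delta method gives SE(λ) = SE(β2)/β1. For this design the within-subject least-squares variance factor of β2 is 2.334, so SE(λ) = 10 × √2.334 / 300 = 0.0509.

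**3. Additive drift: third dose 12 mg/dL below the first.** The three dose-number effects deviate from their mean by +6, 0 and −6, a mean square of (36 + 0 + 36)/3 = 24.
- Sum of squares left in the error: 162 × 24 = 3,888.
- Residual df: 162 − 18 − 2 = 142, so the residual variance becomes 100 + 3,888/142 = 127.4.
- Reported SE(λ) = √127.4 × √2.334 / 300 = 0.0575. The ratio to 0.0509 is 1.13; simulated SEs rounded to 0.057 and 0.051 give 1.12.
- λ itself is unchanged (1.000 in noise-free data). With dose number fitted, the residual variance returns to 100 at a cost of 2 of 142 df.

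**4. Proportional drift: response 15% smaller at dose 2 and 30% smaller at dose 3.** The mean slope falls to 0.85 of its value, so the actual spread of λ is 0.0509/0.85 = 0.060. The simulated reported SE is 0.064, and 0.064/0.060 = 1.07. Dose number alone brings the SE to 0.062; the rest needs its interaction with dose. λ is again unbiased.

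**5. A noisier setting (SD 15).** The 90% half-width for λ is 0.127 with no drift. It becomes 0.133, 0.147 and 0.169 when the response falls 5, 10 and 15 units per dose number, which is 5%, 16% and 33% wider. Coverage rises to about 90%, 94% and 96%. The dose-number term returns all three to 0.127.

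**6. Carry-over from the preceding same-day dose.** There are 9 × 8 = 72 ordered treatment pairs, but only 9 × 3 × 2 = 54 neighbours fall within a day, so preceding dose is not balanced. The mean same-day preceding dose ranges from 220/6 = 36.7 µg (before 200 µg LY3185643) to 600/6 = 100 µg (before 50 µg rGlucagon). If a preceding 200 µg lowers the next response by 10 or 20 units, in proportion for smaller doses, noise-free λ is 0.994 or 0.988. It is the same with or without the dose-number term, and 1.000 with a previous-dose term. For true λ = 1.25 with the 20-unit effect, simulated λ is 1.225.

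**7. Could first doses alone check the washout?** They give 54 profiles, three per subject, and an SE for λ of about 0.11. The shift to be detected is about 0.01 to 0.02, so agreement with the full-data λ would show nothing.

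**The case against.** The strongest reply is that this is a refinement of precision with a conservative consequence. The interval is too wide, not too narrow, and no margin or decision threshold is attached to λ. Baseline is reset before each dose, so a shift in fasting level is partly removed from change-from-baseline and incremental parameters. The additive figure therefore applies to drift in the response itself or to unadjusted Cmax. The protocol cites evidence against attenuation, and protocol 3.2.1 reports LY3185643 below quantification by 4 hours and glycemic effects lasting up to 3 hours. All of this stands and limits the weight of the point. It does not show that responsiveness is constant over a lengthening fast, and the term costs almost nothing if it is.

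A reader might infer more than the documents support:
- **That λ is biased by drift.** The example table is balanced, so it is not, in completers.
- **That drop-out overturns this.** Replacements take over the discontinued subject's sequence. With half of subjects leaving early at random (SD 15, a fall of 10 units per dose number and the 20-unit carry-over), mean λ was 0.991. The cost was again width: a half-width of 0.195, against 0.156 with dose number and 0.152 with previous dose as well. The documents give no drop-out rate.
- **That the protocol itself predicts blunted later doses.** The remark that the transient effect "likely reflects a feedback inhibition of hepatic glucose output in response to exogenous glucagon administration" concerns high LY3185643 concentrations and follows text on doses above 0.2 mg, beyond this trial's range.
- **That injection site is confounded with dose number.** The protocol says "Each injection in a given study period will be administered into a different quadrant of the anterior abdominal wall" but fixes no order.
- **That the model cannot be fitted because it allows one dose per period.** That is loose notation; all nine profiles can enter it.

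**Conclusion.** The omission is real and worth correcting, and its effect is modest. With the example sequences and complete data, a common within-day drift leaves λ unbiased and widens its 90% CI. The excess is about 12 to 13% for a 12 mg/dL third-dose loss, about 5 to 7% for a 30% smaller third-dose response, and close to nil without drift. These figures rest on an assumed 60 mg/dL linear response at 200 µg, SD 10 mg/dL and λ = 1, and on an actual schedule as balanced as the example. The true drift cannot be derived from the documents.

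Carry-over that depends on the preceding dose is distinct. It could move λ by about 1 to 2% in the scenarios tried, and a dose-number term does not remove it. A reader might conclude that the 4-hour washout fails. Nothing in the documents shows that; they show only that no analysis is planned to confirm it, although the samples would allow one.

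**What to change.** In SAP 9.4.2:
- Index observations by subject, period and dose number within the day, and correct the definition of d to match.
- Add dose number (1, 2, 3) as a fixed effect in the model for every PD parameter. Add its interaction with dose if not negligible, parameterised as a common scaling of both treatments' slopes so that a single λ is kept.
- As the washout check, prespecify a sensitivity model with a term for the preceding same-day dose (zero for the first dose of the day). Tabulate predose glucose, C-peptide and drug concentrations by dose number and by preceding dose.
- Do not use λ from first doses only as that check.

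The cost is 2 df for dose number, 2 for the interaction and 1 for the previous dose (5 in all), one extra model run and one table. No new data are needed.
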